2.1 Trial Design

The N-DOSE AD study is designed as a randomized, double blind, placebo-controlled, parallel-group, multi-centre, phase II dose-optimization study. Treatment allocation is a 1:1:2 ratio. Patients are randomized to either placebo, dose escalation up to 3000 mg NR or stable dose of 1000 mg NR for three months.

2.2 Randomisation

Eligible patients are allocated in a 1:1:2 ratio between placebo, DS and DE groups, using the electronic case report form (eCRF) vieDoc.com (www.viedoc.com, version 4.77.8648.13864).

The randomization process is described in full within the clinical trial protocol. Details of the randomization including the final random allocation list are held securely and unavailable to unauthorized trial personnel.

2.3 Statistical Framework

2.3.1 Hypothesis Test

This trial is designed to investigate the dose-responsiveness of NR treatment in a dose escalation group compared to a dose stable group and compared to placebo over three months.

The primary null hypothesis (H₀) is that the NR-induced increase in cerebral NAD levels (measured by ³¹P-MRS) is not dose-responsive.

The alternative hypothesis (HA) is that NR-induced increase in cerebral NAD levels is dose responsive.

There is only one identified primary analysis in this trial. All other efficacy analyses will be regarded as secondary or exploratory.

2.3.2 Confidence Intervals and p-values

All calculated p-values will be two-sided and compared to a 5% significance level. If a p-value is less than 0.05, the corresponding treatment group difference will be denoted as statistically significant. All efficacy estimates will be presented with two-sided 95% confidence intervals. As there is only one primary null hypothesis to be tested in this trial, there will be no adjustments for multiplicity.

2.3.3 Decision Rule

This trial is designed to address a single primary outcome. Non-inferiority is claimed if the primary null hypothesis is rejected on the significance level (alpha) of 0.025 (one-sided). That is, if the upper limit of the 95% two-sided confidence interval for the treatment difference is less than 15%.

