## **10 STATISTICAL METHODS AND DATA ANALYSIS**

## **10.1 Determination of Sample Size**

Our primary null hypothesis ( $H_0$ ) is that the NR-induced increases in cerebral NAD levels (measured by 31P-MRS) are not dose-responsive. The alternative hypothesis (HA) is that this measure is dose responsive. In the NADPARK study, all three measures showed a highly significant increase in the group

receiving 1000 mg NR (n = 15) compared to the placebo group (n = 15). In the NADPARK study25, treatment with 1000mg of NR led to an increase in cerebral NAD-levels by a factor of 1.27 from baseline in the treatment group, whereas the change in the placebo group was negligible at -0.43%. Under the HA, we assume that cerebral NAD levels will increase in a linear fashion in the 2000 mg NR and 3000 mg NR groups, respectively. Based on these assumptions and given a type I error rate of 5% ( $\alpha$  = 0.05) and a type II error rate of 10% ( $\beta$  = 0.1, power = 90%), we estimated that a sample size of 30 individuals will be required in the dose escalation group. Accounting for drop-out and statistical safety margin, we estimate that the study requires 40 subjects in this group.

For the secondary and exploratory outcomes, we assume that the metabolomic, transcriptomic and inflammatory cytokine analyses will have sufficient power, since they produced very large effect sizes and highly significant results in the NADPARK study with 15 individuals per group. Since no pilot data exist for the proteomic and epigenomic analyses, these will be exploratory in nature. However, in our previous experience, a sample size of 20 per group should be sufficient to detect treatment-induced differences of biological relevance.

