## 10.4 Planned analyses

All statistical analysis is planned after the completion of the study.

All randomized patients will be included in the primary analyses. All randomized patients will be included in the primary analyses and sensitivity analyses will be carried out comparing results from the ITT, SAS and PPS data sets. In the case of missing assessments, the subject will be included if possible.

The *primary analysis* of the primary endpoint will be performed using analysis of covariance (ANCOVA) between the dose stable (DS-group) and dose escalation group (DS-group), i.e. the regression of NAD levels measured by P-MRS at week 12 depending on randomization group and adjusted for P-MRS at baseline. No additional adjustments/covariates will be used. As this is the single primary outcome, alpha will be set at 0.05. No correction for multiple testing will be performed.

The *secondary analysis* of the primary endpoint will be the comparison of change over time from baseline to week 4, week 8 and week 12, between the DE-group and the DS-group. This will be assessed using a linear mixed model (LME), i.e. NAD (P-MRS) at weeks 4,8 and 12 depending on randomization group, time and their interaction adjusted for random individual intercept.

The *primary analysis* of the secondary endpoint will be performed using ANCOVA between the dose stable (DS-group) and dose escalation group (DS-group), i.e. the regression of NAD or NAD metabolite levels measured by HPLC-MS at week 12 depending on randomization group and adjusted for NAD or NAD metabolite at baseline. No additional adjustments/covariates will be used.

The analysis of exploratory endpoints will be performed in a similar manner as for the primary and secondary endpoints. ANCOVA will be used to compare endpoints at week 12, and LME will be used to compare change from baseline to week 4, week 8 and week 12.

In addition, for PET analyses, changes in network scores with treatment will be evaluated for each group separately using permutation tests. Relationships between network values, brain NAD levels and cognitive ratings or between treatment-related changes in these variables will be evaluated using Pearson's product-moment correlations, whereas Spearman rank-order correlation coefficients will be computed for non-normally distributed variables.

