5.1.2 Primary Inferential Analysis

The ***primary analysis*** of the ***primary endpoint*** will be performed using analysis of covariance (ANCOVA) between the dose stable (DS-group) and dose escalation group (DE-group), i.e. the regression of NAD levels measured by ^{31}P -MRS at week 12 depending on randomization group and adjusted for ^{31}P -MRS at baseline. No additional adjustments/covariates will be used. As this is the single primary outcome, alpha will be set at 0.05. No correction for multiple testing will be performed.

The formula for this calculation in R is:

```
lm_object = lm(NAD_at_V4 ~ Group + NAD_at_V1)
```

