5.1.7 Secondary Analyses of the Primary Endpoint

The *secondary analyses* of the *primary endpoint* will be:

1. Analysis of covariance (ANCOVA) between the dose stable (DS-group) and placebo group group (PL-group), i.e. the regression of NAD levels measured by ^{31}P -MRS at week 12 depending on randomization group and adjusted for ^{31}P -MRS at baseline. No additional adjustments/covariates will be used. No correction for multiple testing will be performed.

The above-mentioned analysis will be performed in the same manner as the primary analysis for the primary endpoint.

2. Comparison of change over time from baseline to week 4, week 8 and week 12, between the DE-group, DS-group and the PL-group. This will be assessed using a linear mixed model (LME), i.e. NAD (^{31}P -MRS) at weeks 4, 8 and 12 depending on randomization group, time and their interaction adjusted for random individual intercept. The above-mentioned analysis will be performed using a linear mixed model (LME) comparing NAD level as a function of group with time and the interaction between group and time as independent variables. Individual subjects will be random effects.

The following formula will be used in R format:

```
NAD_level ~ Group + Visit + Group * Visit + (1 | Subject)
```

Visit will be treated as a numeric variable if there is no plateau effect. If there is a plateau effect in the data, visit will be treated as a factor.

The primary effect estimate will be the B-coefficient with confidence intervals and Cohen's d. Cohen's d will be calculated as the difference in the means between two groups and divided by the pooled standard deviation.

The dose stable group will be set as the reference to which the dose escalation and placebo groups will be compared.

No additional covariates will be included in the LME model.

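### SAP 2.3.3 sets a non-inferiority rule with an undefined 15% margin that contradicts the planned two-sided dose-response test and cannot show dose-response whichever way the difference is taken

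*SAP*

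**What the plan says.** Most of the plan describes one ordinary test of a difference.

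- SAP 2.3.1 sets a null of no dose-response: "The alternative hypothesis (HA) is that NR-induced increase in cerebral NAD levels is dose responsive".
- SAP 2.3.2 makes all p-values two-sided at 5%: "If a p-value is less than 0.05, the corresponding treatment group difference will be denoted as statistically significant".
- SAP 5.1.2 fits "lm_object = lm(NAD_at_V4 ~ Group + NAD_at_V1"), comparing DE with DS at week 12 with baseline as covariate. Protocol 10.4 gives the same ANCOVA and says "As this is the single primary outcome, alpha will be set at 0.05".
- SAP 5.1.3 reports the coefficient with its confidence interval, and Cohen's d.

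SAP 2.3.3 (Decision Rule) says something else: "Non-inferiority is claimed if the primary null hypothesis is rejected on the significance level (alpha) of 0.025 (one-sided"). The criterion it attaches to this claim is a bound on the interval, met "if the upper limit of the 95% two-sided confidence interval for the treatment difference is less than 15" per cent.

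The only statement about a reference group is in SAP 5.1.7 and concerns the secondary mixed model: "The dose stable group will be set as the reference to which the dose escalation and placebo groups will be compared".

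**The concern.** The SAP contains two success criteria for its single primary analysis, and no text ranks one above the other. Rejecting a null of no dose-response does not establish non-inferiority, and meeting a non-inferiority margin does not establish dose-response.

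The rule also cannot be applied as written, for two reasons.

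- **Direction.** The treatment difference is not defined as DE minus DS or as DS minus DE. The 5.1.2 code sets no reference level. If the groups are labelled DE and DS, R's default alphabetical order makes DE the reference and the coefficient DS minus DE. Carrying over the reference in 5.1.7 gives the opposite sign.
- **Scale.** The coefficient is in NAD/ATP-α units, and no percentage difference is defined anywhere as the quantity to be estimated.

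A reader who goes to 2.3.3 to judge the trial could reach a different verdict from the planned test. With direction and scale open, a reading could be chosen after the data are seen.

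**Working it through.** **1. The plan's own figures.** One-sided 0.025 and a two-sided 95% interval use the same critical value, 1.960, so the alpha level in 2.3.3 is internally consistent and is not the fault. The rule has no sample size of its own. The stated 30 patients in the DE group (protocol 10.1, SAP 5.5) can be neither reproduced nor refuted, because no SD is given. At a DE–DS difference of 54 points, two-sided 5% and 90% power, it would imply an SD of 52.7 points (15 DS, 30 DE) to 64.5 points (30 and 30).

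**2. Logic, with no numbers assumed.**

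- If the difference is DE minus DS, an upper limit below 15% rules out a large advantage of escalation. The hoped-for result fails.
- If it is DS minus DE, an upper limit below 15% shows only that DE is not worse than DS by 15% or more. That is compatible with no dose effect.

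Neither reading tests dose-response.

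**3. Inputs for the size of the effect.**

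- Planned allocation: 40 DE, 20 DS.
- Planning effect: 1000 mg "led to an increase in cerebral NAD-levels by a factor of 1.27 from baseline in the treatment group" (protocol 10.1), with a linear rise assumed. Read as +27 points of baseline per 1000 mg, DE minus DS = 81 − 27 = +54 points.
- SD, not given in the documents: protocol 1.1.3 reports a paired t-test with P = 0.016 and mentions 13 patients. t(12) = 2.801; 2.801/√13 = 0.777; SD = 0.27/0.777 = 0.347. The 90% limits by chi-square on 12 df are 0.263 and 0.527. With n = 15 instead, t(14) = 2.739 and the SD is 0.382.
- 15% is read as 0.15 of baseline.

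**4. Worked case at SD 0.347.** SE = 0.347 × √(1/40 + 1/20) = 0.347 × 0.274 = 0.095. With 57 df the half-width is 2.002 × 0.095 = 0.190. The upper limit is below 0.15 when the estimate is below 0.15 − 0.190 = −0.040. With no true difference that has probability Φ(−0.040/0.095) ≈ 34%. By symmetry it is the same for either subtraction order.

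**5. Simulation (400,000 trials per setting, SE estimated).** Percentage of trials meeting each rule:

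| True DE − DS | Rule | SD 0.263 | SD 0.347 | SD 0.527 |
|---|---|---|---|---|
| 0 | 2.3.3, either order | 54 | 34 | 17 |
| 0 | 95% CI above zero | 2.5 | 2.5 | 2.5 |
| +0.54 | 2.3.3 as DE − DS | 0 | 0 | 0 |
| +0.54 | 2.3.3 as DS − DE | 100 | 100 | 99.7 |
| +0.54 | 95% CI above zero | 100 | 100 | 96 |
| −0.27 | 2.3.3 as DE − DS | 100 | 99 | 82 |
| −0.27 | 2.3.3 as DS − DE | 0.0 | 0.1 | 0.3 |

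**6. Sensitivity of the no-difference rate.**

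- SD 0.382 (n = 15 in the pilot): 29%.
- SD 0.15: 95%.
- 30 DE and 15 DS completers: 42%, 27% and 14% at the three SDs in the table.
- 15% read as a share of the DS week-12 mean (0.15 × 1.27 = 0.1905): 74%, 50% and 25%.

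**The case against.** The strongest reply is that 2.3.3 is one isolated paragraph, probably left over from elsewhere, against several consistent ones. The contrast, time point, model, alpha and interval are fixed in SAP 1.3.1, 2.3.1, 2.3.2, 5.1.2 and 5.1.3 and in protocol 10.4. A switch to non-inferiority would visibly contradict them. That lowers the risk of misuse, but the documents do not call the paragraph an error or say which section prevails.

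The numerical objections are fair as far as they go. The SD is a paired-change SD from Parkinson's disease standing in for an ANCOVA residual SD in Alzheimer's disease. The documents do not say that the t-test used 13 patients, nor how the factor 1.27 was averaged. Both readings of 15% are guesses. At the larger SDs the rule is usually not met when the doses do not differ, so one should say that it can be met, not that it is. These points move the rates but do not affect step 2.

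Two further points stand. The reference level does not change a two-sided p-value, so under the planned test it affects only the sign reported. And requiring the interval to lie above zero adds a direction to the two-sided wording of 2.3.2; it is compatible with that test but is a choice.

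**Conclusion.** The concern holds and must be fixed. SAP 2.3.3 contradicts the hypothesis, the two-sided level and the primary ANCOVA stated elsewhere. It has neither a subtraction order nor a usable scale, and under neither order does meeting it show dose-response. That conclusion rests on the text alone.

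The size rests on a borrowed SD, on 15% read as points of baseline, and on no dropout. On those terms the no-difference rate is about 7 to 21 times the 2.5% of an interval-above-zero rule (17.4/2.5 to 53.6/2.5). With 30 and 15 completers the lowest rate is still 14%. At the planned +54 points, the DE minus DS reading would call a clear success a failure in essentially every trial.

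**What to change.** Replace SAP 2.3.3 with: *Dose-responsiveness is claimed if the two-sided 95% confidence interval for the DE minus DS coefficient at week 12 (ANCOVA of section 5.1.2, DS as reference level) lies entirely above zero. An interval entirely below zero is reported as a difference against escalation, not as dose-responsiveness.* Delete the non-inferiority wording and the 15% margin.

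In the 5.1.2 code, set the reference explicitly, for example `Group = relevel(factor(Group), ref = 'DS')`, to agree with 5.1.7.

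The cost is one paragraph and one line of code, with no new data or patients. SAP 4.4 and 6.2 describe data collection in the past tense, so state the date of the change relative to unblinding. If unblinding has already occurred, report it as a dated correction.

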2.4 Timing of Outcome Assessments

For all clinically planned measures, visits should occur within a window of the scheduled visit. Visits outside visit window is regarded as a protocol deviation. Visits more than 7 days outside the visit window are regarded as a major protocol deviation. The target day and visit window are defined in the protocol as:

Visit Label	Target Day	Definition (Hour window)
Screening	-90 Days	Prior to V1 (Baseline)
V1 (Baseline)	Day 0	Day 0
V2 (Week 4)	Day 28	Target day \pm 72 hours
V3 (Week 8)	Day 56	Target day \pm 72 hours
Last study visit* (Week 12)	Day 84	Target day \pm 72 hours

*The last study visit is defined as the visit following the last visit with randomised treatment, and where there is a study end statement.

For analysis and tabulation purposes, we define study time points as

Time Point Label	Target Day	Definition (Day window)
V1 (Baseline)	Day 0 (Randomisation)	Information up to randomisation

V2 (Week 4)	28	Days 25 to 31
V3 (Week 8)	56	Days 53 to 59
V4 (Week 12)	84	Days 81 to 87

If more than one visit fall into the same time point interval, information on all visits will be used in the analyses.

2.5 Statistical Interim Analyses and Stopping Guidance

There will be no interim analyses in this trial due to the short duration for each participant and relatively small sample size.

2.6 Timing of Main Analysis

The main analysis is planned when all participants have concluded 84 ± 7 days of treatment, all data up to 84 days have been entered, verified and validated and the primary database has been locked.

3 Trial Population

3.1 Screening Data, Eligibility and Recruitment

The total number of screened patients and reasons for not entering the trial will be summarised and tabulated.

A CONSORT flow diagram will be used to summarise the number of patients who were:

- assessed for eligibility at screening
- eligible at screening
- ineligible at screening*
- eligible and randomised
- eligible but not randomised*
- received the randomised allocation
- did not receive the randomised allocation*
- lost to follow-up*
- discontinued the intervention*
- randomised and included in the primary analysis
- randomised and excluded from the primary analysis*

*Reasons will be provided.

Inclusion criteria:

The following condition must apply to the prospective patient at screening prior to receiving study agent:

- Diagnosis of probable AD according to the core clinical criteria updated in the NIA and Alzheimer's Association guidelines¹⁰.
- Biomarker evidence consistent with AD neuropathologic change, defined by CSF markers.
- Diagnosed with AD within two years from enrollment.
- CDR 0.5-1 (inclusive) at enrolment¹¹.
- Age 50 to 85 years (inclusive) at the time of enrollment.
- A study partner able to study data and assist the participant in the study drug administration, i.e. contact \geq 3 times weekly.
- Capacity to provide written informed consent for study participation defined as Montreal Cognitive Assessment (MoCA) score \geq 16¹², or Mini Mental State Evaluation (MMSE) score \geq 20¹³. MMSE or MoCA must have been performed within 6 months prior to baseline. If there is any doubt regarding the participants capacity to give informed consent we will ask for an independent evaluation by a consultant clinician who is not associated with the N-DOSE AD study.
- Cholinesterase inhibitors and memantine can be used if stable for 8 weeks prior to baseline visit.
- Able to undergo lumbar puncture
- Able to undergo MRI

Exclusion criteria:

The participant cannot have any of the following prior to receiving study agent:

- Diagnosis of dementia other than probable AD.
- Comorbidity that precludes study participation or data interpretation.
- Any psychiatric disorder that would interfere with compliance in the study.
- Any severe somatic illness that would interfere with compliance and participation in the study.
- Use of high dose vitamin B3 supplementation within 30 days of enrollment.
- Metabolic, neoplastic, or other physically or mentally debilitating disorder at baseline visit.
- Current treatment with Oral Anticoagulation Therapies
- Implants that preclude MRI examinations, e.g. DBS, pacemaker

3.2 Baseline Patient Characteristics

The patient demographics and baseline characteristics to be summarized include:

- Age (in years).
- Sex (assigned according to electronic patient records).
- Weight (in kilograms).
- Height (in centimeters).
- BMI (in kg/m^2).
- Time since diagnosis
- Time since onset of symptoms
- Current use of medication for symptoms of Alzheimer's diseaseADAS-Cog 13 score.
- CDR-SB.

- CDR-global
- MoCA score.
- TMT A and B score.
- IADL and PADL score.
- MADRS score.
- NPI-Q score.

Patient demographics and baseline characteristics will be summarized by randomized treatment arm and overall using descriptive statistics (N, mean, standard deviation) for continuous variables, and number and percentages of patients for categorical variables. No formal statistical analysis will be performed between groups as participants were randomized during the trial.

3.3 Withdrawal/Follow-up

The status of eligible and randomised patients at trial end will be tabulated by treatment group according to

- completed intervention and assessments
- completed assessments but not intervention
- withdrew consent
- lost to follow-up

3.4 Adherence and Protocol Deviations

3.4.1 Adherence to Allocated Treatment

Compliance is assessed based on the percentage of subjects who have taken the scheduled number of pills. It is defined as:

% compliance = (number of capsules taken / number of capsules supposed to have been taken) x 100%.

The number of capsules supposed to have been taken will be calculated as the duration of treatment (end of study medication – start of study medication) multiplied by 12 per dispensation of study medication. In this study 6 capsules are taken in the morning and 6 capsules in the evening.

The mean \pm SD of study drug compliance over the whole study period and between individual visits will be presented in a table by treatment group.

3.4.2 Protocol Deviations

The following are pre-defined major protocol deviations regarded to affect the efficacy of the intervention:

- Entering the trial when the eligibility criteria should have prevented trial entry.
- Discontinuation of intervention prior to 84 ± 7 days.
- Major change in concomitant choline-esterase or memantine treatment.
- Received or used other intervention than allocated.
- Adherence to allocated treatment below 80%.

- Visit date interval larger than 28 ± 7 days between individual visits (i.e.: V1 and V2, V2 and V3, and V3 and V4).
- Visit date interval larger than 84 ± 7 days from V1 to V4.
- Not fasting before neuroimaging with blood glucose > 8

Protocol deviations are classified prior to unblinding of treatment. The number (and percentage) of patients with major and minor protocol deviations will be summarized by treatment group with details of type of deviation provided. The patients that are included in the FAS analysis data set (see point 3.5 below) will be used as the denominator to calculate the percentages. No formal statistical testing will be undertaken.

3.5 Analysis Populations

The Full Analysis Set (FAS) will be performed using the intention to treat population, defined as all patients randomly assigned to a treatment group and attended the baseline visit.

The Safety Analysis Set will include all patients having received at least one dose of study treatment after randomisation.

The Per Protocol Analysis Set (PPS) will include all randomised patients meeting the study eligibility criteria and with no major protocol deviations affecting the treatment efficacy.

4 Endpoint Definitions

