## **10.3 Population for Analysis**

Intention to treat (ITT)/Full analysis set (FAS) population: All participants, regardless of protocol adherence.

The Safety Analysis Set (SAS) will include all patients having received at least one study treatment infusion after randomisation.

The Per Protocol Analysis Set (PPS) will include all randomized patients meeting the study eligibility criteria and with no major protocol deviations affecting the treatment efficacy.

The following are pre-defined major protocol deviations regarded to affect the efficacy of the intervention:

- Entering the trial when the eligibility criteria should have prevented trial entry.
- Discontinuation of intervention prior to  $84 \pm 7$  days.
- Received or used other intervention than allocated.
- Adherence to allocated treatment below 80%.
- Visit date interval larger than  $28 \pm 7$  days between individual visits (i.e.: V1 and V2, V2 and V3 and V3 and V4)\*.
- Visit date interval larger than  $84 \pm 7$  days from V1 to V4\*.
- Not fasting before neuroimaging.

\*Due to updated findings from a pharmacokinetic study (ClinicalTrials.gov, NCT: NCT05698771, in revision) that NAD levels increase and reach a plateau within 1-2 weeks of NR treatment both in healthy

individuals and persons with Parkinson's disease. A 3 week period should therefore be sufficient to assess the effects of increasing NR dosage.

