#### **Protocol:**

#### **Participant preparation:**

The participant should fast a minimum of 6 hours before injection of 18F-FDG. A peripheral venous catheter (PVC) is then placed in the medial cubital vein. Blood glucose is measured. The required blood glucose level is below 8 mmol/L. 30 minutes before the scan 250 MBq of 18F-FDG is injected into the PVC. The participant is required to lie in a quiet, dark environment during the interval after injection and before scanning to minimize brain activity. The participants should not use mobile phones or headphones during this period. Eyes must be closed for fMRI sequences. Imaging is to be taken up to 72 hours before or after physical examination of participants.

Positioning: Localizer Auto align if possible

Scan parameters: Scan labelled by study ID.

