5.1.6 Sensitivity Analyses

Sensitivity analysis will be performed by comparing the results of analysis with the FAS and PPS populations. If there is a notable difference this will be commented upon.

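### One per-protocol set for all endpoints can drop a usable baseline/week-12 31P-MRS pair because of an event at week 4 or week 8

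*SAP*

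**What the plan says.** SAP 3.5 defines one PPS, at patient level: it "will include all randomised patients meeting the study eligibility criteria and with no major protocol deviations affecting the treatment efficacy". SAP 3.4.2 opens its list with "The following are pre-defined major protocol deviations regarded to affect the efficacy of the intervention", so every item on the list excludes the patient and no case-by-case filter is left. Two items matter here:

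- Timing: "Visit date interval larger than 28 ± 7 days between individual visits (i.e.: V1 and V2, V2 and V3, and V3 and V4". A separate item limits V1 to V4 to 84 ± 7 days.
- Fasting: "Not fasting before neuroimaging with blood glucose > 8". No visit and no imaging modality is named. Protocol 10.3 has the shorter "Not fasting before neuroimaging", with no glucose condition.

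For the primary endpoint, SAP 5.1.6 states: "Sensitivity analysis will be performed by comparing the results of analysis with the FAS and PPS populations". The same PPS is used for the CSF endpoint (SAP 5.2.6) and for adverse events (SAP 6.1.2). Protocol 10.4 adds the safety set to the comparison.

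The primary analysis (SAP 5.1.2 and 5.1.5) regresses the week-12 value on group and baseline, so it uses V1 and V4 only. The stated source of the fasting requirement is Appendix B: "The participant should fast a minimum of 6 hours before injection of 18F-FDG".

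**The concern.** A per-protocol comparison should show whether the result holds among patients in whom the dose contrast was delivered and measured as planned. Here a patient can leave the set because of an event at a visit that contributes nothing to the week-12 comparison. Such exclusions reduce a dose-stable arm of only 20 and widen the PPS interval. They also make any FAS-PPS difference partly chance, when it is meant to reflect adherence. Since SAP 5.1.5 drops patients without a V4 value and SAP 5.1.6 plans nothing beyond FAS versus PPS, this comparison is the SAP's only robustness check on the primary result.

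**Working it through.** The plan gives no deviation rate and no expected PPS size, so there is no stated figure to reproduce. The first three steps are logical; the last two rest on assumed rates.

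**1. Visit gaps.** The limit is 28 + 7 = 35 days per gap and 84 + 7 = 91 days in total. Visits on days 0, 36, 60 and 84 give gaps of 36, 24 and 24 days, with V4 exactly on target. Because 36 > 35, the patient leaves the PPS although the V1/V4 pair is valid.

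The V1-V4 limit restricts how often this happens. A 36-day first gap followed by two 28-day gaps gives 36 + 28 + 28 = 92 > 91, so that patient is excluded whatever is done about the individual gaps. A week-12 scan on that day would also count as missing under SAP 5.1.5. After a 36-day first gap the other two may total at most 91 - 36 = 55 days, so at least one must be shorter than 28 days. Only patients whose later visits were compressed can be recovered.

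**2. Fasting.** Imaging takes place at V1, V2, V3 and V4 (protocol 6.1). A fasting lapse with glucose above 8 at V2 or V3 excludes the patient from the PPS for every endpoint. That includes the V1/V4 31P-MRS pair and the CSF comparison, which uses no scan.

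**3. Two internal mismatches.**
- Protocol 10.3 counts non-fasting alone; SAP 3.4.2 counts it only together with glucose above 8.
- SAP 2.4 sets V2 at day 28 ± 72 hours (days 25 to 31) and calls a visit major only when it is more than 7 days outside that window, that is, after day 38. Under SAP 3.4.2 a V1-V2 gap above 35 days is already major. V2 on days 36 to 38 is therefore not major under one section and major under the other.

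**4. Size if only visit gaps fail.** Assume each of the three gaps fails independently with probability q, equally in both arms. The current rule keeps (1-q)³. A rule counting only V3-V4 keeps (1-q). With the standard error proportional to 1/√n, the ratio is √[(1-q)/(1-q)³] = 1/(1-q).

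| q (assumed) | Current rule keeps | V3-V4 only keeps | SE ratio |
|---|---|---|---|
| 3% | 0.913 | 0.970 | 1.03 |
| 5% | 0.857 | 0.950 | 1.05 |
| 10% | 0.729 | 0.900 | 1.11 |

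At 5%, from 40 dose-escalation and 20 dose-stable patients, this is about 34 and 17 against 38 and 19. These ratios are upper bounds: by step 1, many patients with a long early gap also breach the V1-V4 limit, which stays. Clustering of failures in the same patients would reduce them further.

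**5. Adding fasting/glucose events.** With an independent rate f per session, the current rule multiplies retention by (1-f)⁴. Counting V1 and V4 only gives (1-f)²; not counting the item for 31P-MRS gives 1. The extra SE factor is 1/(1-f) or 1/(1-f)². For illustration, f = 1% with q = 5% gives 1.053 × 1.010 = 1.06 or 1.053 × 1.020 = 1.07. Nothing in the documents indicates what f is.

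**The case against.** A single patient-level PPS is an ordinary convention. The primary FAS analysis keeps every valid pair, and the PPS comparison carries no decision rule: a notable difference is only commented upon. Deviations are classified before unblinding, so the rule brings in no unblinded selection. Protocol 10.4 also names the safety set. All of this stands and limits the weight of the point. The safety set, however, requires only one dose taken, so it is close to the FAS and does not test adherence.

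The interval rules can also be defended as describing adherence to the escalation schedule, and the V2 and V3 values do enter the mixed model of the same endpoint (SAP 5.1.7). This is why the early-gap part is more debatable than the fasting part. Likewise, 31P-MRS and PET share a session (protocol 7.4) and the item refers to neuroimaging in general, so the sponsor may have a reason to count fasting for 31P-MRS. The documents give none, but they do not rule it out.

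Three stronger readings are tempting and are not supported.

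- A reader might infer that any non-fasting week-4 PET removes the patient. That follows from the protocol list only. The SAP, to which protocol 10.4 refers for analysis details, requires the lapse together with glucose above 8, and Appendix B requires glucose below 8 mmol/L for the scan. The joint event is likely to be rarer.
- A reader might give fasting events the same rate as visit gaps. At 5% for all seven checks, retention is 0.95⁷ = 0.698, and the excess standard error is √(0.857/0.698) = 1.11 to √(0.950/0.698) = 1.17. That treats the joint event as being as common as a late visit, and it leaves out the V1-V4 limit.
- A reader might take the footnote to protocol 10.3 ("A 3 week period should therefore be sufficient to assess the effects of increasing NR dosage") as proof that an early long gap leaves week-12 brain NAD unchanged. It reports NAD levels reaching a plateau in healthy people and in Parkinson's disease, and names neither brain nor Alzheimer's disease. It makes the case for excluding such patients weaker; it does not settle it.

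**Conclusion.** The structural point holds: one patient-level PPS serves all endpoints, and an event at V2 or V3, or an early long gap with V4 on time, can remove a valid V1/V4 31P-MRS pair from the SAP's only named sensitivity comparison. The consequence is modest. The primary result is untouched, and on visit gaps alone the PPS standard error is at most about 3%, 5% or 11% larger than needed at assumed failure rates of 3%, 5% or 10% per gap. These figures assume independent failures, equal loss in both arms and an unchanged residual standard deviation. Fasting/glucose events would add to them by an amount the documents do not allow one to estimate. This is a small, cheap improvement to a supportive analysis. The fasting part is the firmer of the two, because a V2 or V3 scan is not used in the week-12 ANCOVA at all.

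**What to change.** Before unblinding, amend SAP 3.4.2 and 3.5 as follows.

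- Apply the fasting/glucose item only to the scans used in the analysis concerned: V1 and V4 for the week-12 ANCOVA, and only that visit's value in the mixed model. Limit it to FDG-PET unless the sponsor gives a reason to count it for 31P-MRS.
- For the week-12 endpoints, count the V3-V4 and V1-V4 timing. Apply the V1-V2 and V2-V3 gaps to the V2 and V3 values, or state why an early gap should exclude the week-12 pair.
- Leave the eligibility, allocation, adherence and discontinuation items at patient level.
- Reconcile the fasting item between protocol 10.3 and SAP 3.4.2, and the definition of a major timing deviation between SAP 2.4 and SAP 3.4.2.

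The cost is a change of wording. The downside is that PPS size will differ by endpoint and must be reported for each.
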